8.3.5.9. Missing Data

Laboratory values below the level of quantification (BLQ) will be set to one-half the limit of quantification (unless noted otherwise) in computations for the aggregate analyses, but will be noted as BLQ in the listings. Laboratory values that are missing will be excluded from computations for the aggregate analyses and will be noted as missing in listings. On graphs, missing values will be shown by the absence of a data point.

The MMTT is expected to include assessments of C-peptide, glucose and glucagon at -10, 0, 15, 30, 60, 90, and 120 minutes, and AUCs are expected to be based on the assessments from Time 0 through 120 minutes. If one or more of these assessments is missing (note: values reported as BLQ are not considered missing), AUCs will be calculated based on the non-missing data using the trapezoidal rule. If the Time 0 assessment is missing, it will be substituted with the value from the -10 minute time point. For an AUC to be calculated, there must be a minimum of one fasting data point (assessments scheduled for -10 minutes and Time 0), and one post-mixed meal data point (assessments scheduled for 15, 30, 60, 90, and 120 minutes). If this minimum number of data points is not available, the AUC will be recorded as missing. If the MMTT is conducted when the plasma glucose values are out of the range specified, the data will not be included in the analysis and treated as missing.

The primary efficacy analysis employs a repeated-measures model using all follow-up values for all subjects (as described in Section 8.3.5.3.1). Under an MAR assumption where the missing data may depend on the prior observations, i.e., the conditional independence assumption, the model provides unbiased LSmean estimates for the treatment groups at the assessment time points.

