
Primary Statistical Analyses

 ○ Note: the initial parameter values will be used for all parameters in the model (as specified above) with the exception of the covariance matrix of the likelihood function which will use SAS default initial parameters for all chains. ● Initially each chain will run with a simulation size of 50000 (NMC=50000) and all three chains will be included to provide the posterior distribution summaries, treatment differences and construct probability statements (i.e. using a total of 150000 posterior observations). ● SAS provided macros, including %POSTSUM, %TADPLOT and %POSTINT, will be used to provide summaries of the posterior distribution (including 95% HPD credible intervals). ● Thinning will not be used (THIN=1) ● Initially the SAS default of 1000 iterations will be used for the number of burn-in's (NBI=1000) ● For tuning, the following values will be specified: MINTUNE=5, MAXTUNE=500 and NTU=2000. ● Convergence will be assessed using the Gelman & Rubin diagnostic, examining trace plots for model parameters, assessing the Effective Sample Size (ESS) and Geweke diagnostics. The ratio of the Monte Carlo Standard Error (MCSE) to the SD of the posterior will also be assessed. If the model does not converge then the number of burn-in's (NBI), the number of simulations (NMC) and the tuning values may be adjusted, as appropriate, in order to improve model convergence. The numbers by which MCMC iterations and burn-in iterations need to be increased may be significant. Additional adjustments to the model may be necessary if convergence is not improved. ● Historical placebo data from 53 subjects from the DEFEND-1 study will be incorporated as the prior distribution for the Week 52 visit using the robust mixture prior as follows: 
 ○ From DEFEND-1, N = 53 and the mean change from baseline was -0.269, SD = 0.314 and SE = 0.043. ○ The historical prior will be specified as Normal (-0.269, SE=0.043) ○ The weakly informative prior will be specified as Normal (0, SE=1000); ○ $I_{prior} = \log [w * pdf (historical prior) + (1-w) * pdf (weakly informative prior)]$ ○ Prior (week 52 placebo) \sim General (I_{prior}) ● Priors for other parameters (including placebo at other visits) will be specified as Normal (0, var=1E6)
Model Checking & Diagnostics

 ● Convergence of the Bayesian model will be assessed as described above.
Model Results Presentation

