
Sensitivity analyses will be performed without historical DEFEND-1 placebo data and using 100% historical DEFEND-1 placebo data.The analyses will be performed as described for the primary Bayesian analysis, however the robust mixture prior will use values of w=0 and w=1 respectively, rather than w=0.5 (primary analysis).As a further sensitivity analysis, a non-Bayesian repeated measures mixed effect analysis using PROC MIXED will be performed. This model will not include any historical placebo data from the DEFEND-1 study. The analysis will be performed using the MMRM approach, as described for the secondary endpoints in Section 8.1.2 (change from baseline in stimulated (from MMTT) 2 hour plasma C-Peptide AUC at Week 16, 28 and 64)If the amount of missing data is large, the potential impact of missing follow-up data on the conclusions of the primary analysis will be investigated through sensitivity analyses. For example, for each treatment group, the baseline characteristics of the subjects whose Week 52 mixed meal-stimulated C-peptide AUC is missing will be compared with those subjects with available Week 52 mixed meal-stimulated C-peptide AUC data to provide an assessment of the potential for the missing data to cause bias in the conclusions. The report will include presentation of the results of the sensitivity analysis, and a discussion of the implications of both the sensitivity analysis and the comparisons of baseline characteristics on interpreting the conclusions from the primary hypothesis test.

Possible Post-hoc Sensitivity Statistical Analyses:

The following sensitivity analyses are not currently planned to be performed, but may be performed as post-hoc sensitivity analyses if needed

- A sensitivity analysis based on 'on-treatment' observations only may be performed for the primary endpoint Bayesian analysis only (MMRM, MCMC procedure and robust mixture prior).
- For the historical DEFEND-1 placebo data, 'on-treatment' will not be assigned and all previously selected data will be included in the sensitivity analysis. This is due to the fact that the treatment period for DEFEND-1 was only 8 infusions over 8 days at the start of the study.

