
 Reporting for tables, figures and formal statistical analyses: 
 Nominal scheduled visit will be used unless otherwise specified. Planned time relative to dosing will be used in figures, summaries, statistical analyses and calculation of any derived parameters, unless otherwise stated. The impact of any major deviation from the planned assessment times and/or scheduled visit days on the analyses and interpretation of the results will be assessed as appropriate. Reporting for Data Listings: 
 Planned and actual time relative to study drug dosing will be shown in listings (Refer to IDSL Statistical Principle 5.05.1). All data (including unscheduled or unplanned readings) will be presented within the subject's listings.

Reporting Standards	
Unscheduled Visits	

 Unscheduled visits will not be included in summary tables, with the exception of: 
 HbA1c, where unscheduled visits will be used if scheduled assessments are missing and the unscheduled assessments fall in the protocol defined time period for the missing scheduled visit (see Section 11.2). The early withdrawal visit will be handled in the same way as unscheduled visits. Unscheduled visits will be included in laboratory, vital signs and ECG summaries which look at worst-case or maximum values of potential clinical importance or QTC categories. Unscheduled visits will not be included in figures, except as detailed above (including hepatobiliary figures). All unscheduled visits will be included in listings. 	
Descriptive Summary Statistics	
Continuous Data	Refer to IDSL Statistical Principle 6.06.1
Categorical Data	N, n, frequency, %
Reporting of Pharmacokinetic Concentration Data	
Descriptive Summary Statistics	Refer to IDSL Statistical Principle 6.06.1 Assign zero to NQ values (Refer to GUI_51487 for further details)
Reporting of Pharmacokinetic Parameters	
Descriptive Summary Statistics (Log Transformed)	N, n, geometric mean, 95% CI of geometric mean, standard deviation (SD) of logged data and between geometric coefficient of variation (CV _b (%)) will be reported. $CV_b (\%) = \sqrt{(\exp(SD^2) - 1) * 100}$ (SD = SD of log transformed data)
Parameters Not Being Log Transformed	N, n, mean, standard deviation (SD), minimum, median, maximum

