11.5.4. Efficacy

Mixed Meal Tolerance Test (MMTT) Efficacy Endpoints
Stimulated (from MMTT) 2 hour plasma C-peptide AUC

 The C-peptide measurements collected during the 120 minute period following a MMTT are referred to as stimulated C-peptide values. Mixed meal stimulated C-peptide AUC is the area under the C-peptide/time curve from Time 0 to 120 minutes, calculated using the trapezoidal rule. In the computation of the AUC, time will be the nominal sampling time, which will be assigned based on the corresponding visit label in the laboratory results dataset. This reported AUC is normalized for time interval by dividing it by 120 minutes. Note, 120 minutes is used if the result at t=120 is non-missing, otherwise the time difference between first and last times with non-missing results is used. This normalized AUC will be calculated for each subject at Baseline, week 16, week 28, week 52 and week 64. Throughout this document, the term 'C-peptide AUC' refers to time normalized mixed-meal stimulated C-peptide AUC (note: this is equivalent to a weighted mean AUC). Time normalized AUC(0-2H)/weighted mean AUC(0-2H) will be derived for C-peptide and Glucagon Note: time point refers to the nominal sampling time from laboratory data. The weighted mean parameters will be derived by calculating the area under the curve AUC using the trapezoidal rule, and then dividing by the nominal relevant time interval (i.e. $tf - tl$): Weighted Mean $(tf - tl) = \left[\frac{1}{2} \sum_{i=1}^{I-1} (t_{i+1} - t_i)(y_i + y_{i+1}) \right] / [tl - tf]$ Where: y_i = Value of endpoint at ith time point t_i = The ith nominal time point (mins) for MMTT: Before MMTT : $t1=0$ After MMTT : $t2 = 15m, t3 = 30m, t4=60m, t5=90m, t6=120m$ tf = Nominal time point (hrs) of first non-missing obs (in planned time $tf=0h$) tl = Nominal time point (hrs) of last non-missing obs (e.g. in planned time for Glucose, $tl=120m$) I = Number of time points used in the AUC calculation (e.g. $I=6$) If one or more of these assessments is missing (note: values reported as BLQ are not

Mixed Meal Tolerance Test (MMTT) Efficacy Endpoints

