considered missing), AUCs will be calculated based on the non-missing data using the trapezoidal rule. If the Time 0 assessment is missing, it will be substituted with the value from the -10 minute time point. For an AUC to be calculated, there must be a minimum of one fasting data point (assessments scheduled for -10 minutes and Time 0), and one post-mixed meal data point (assessments scheduled for 15, 30, 60, 90, and 120 minutes). If this minimum number of data points is not available, the AUC will be recorded as missing.

- If the MMTT is conducted when the plasma glucose values are out of the range specified, the data will not be included in the analysis and treated as missing. Prior to the MMTT, plasma glucose will be measured using a finger-stick test and must be > 3.9 mmol/L (70 mg/dL) and ≤ 11.1 mmol/L (200 mg/dL) for the data to be included in the analysis. Only the plasma glucose values from the finger-stick test will be used to exclude data from the analysis (no other glucose values will be considered). The MMTT will be treated as missing in the summary/analyses, but will be provided in data listings (along with finger-stick test results).
- Finger-stick glucose results can be identified in the SDTM.LB dataset using LBTEST='Glucose' and VISIT ne " and LBNAM='NOT APPLICABLE - NO RANGES EXPECTED', LBTPT=' ' and LBSPEC='BLOOD'.

Maximum Stimulated C-peptide

- This will be derived as the highest C-peptide value at any time point during the 2 hour MMTT after the subject has ingested the mixed meal.

Plasma Glucagon AUC (0-2hrs)

- This will be calculated as described for C-peptide AUC, but using the plasma glucagon measurements.
- Calculated using nominal times only.

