11.9. Appendix 9: Model Checking and Diagnostics for Statistical Analyses

11.9.1. Statistical Analysis Assumptions

Endpoint(s)	
 Change from baseline in stimulated (from MMTT) 2 hour plasma C-peptide AUC at Week 52
Analysis	
 Bayesian analysis
	
 Convergence will be assessed as described in Section 7.1.2.

Endpoint(s)	
 Change from baseline in stimulated (from MMTT) 2 hour plasma C-peptide AUC Change from baseline in maximum stimulated plasma C-peptide Change from baseline in plasma Glucagon AUC (from MMTT) Change from baseline in HbA1c (%) Change from baseline in body weight (kg) Change from baseline in time spent (h/day) with plasma glucose ≤ 3.9 mmol/L at Week 28 and Week 52; Change from baseline in time spent (h/day) with plasma glucose between >3.9 and 10.0 mmol/L at Week 28 and Week 52; Change from baseline in time spent (h/day) with plasma glucose >10.0 mmol/L at Week 28 and Week 52;
Analysis	
 MMRM
	
 Model assumptions will be applied, but appropriate adjustments maybe made based on the data. The Kenward and Roger method for approximating the denominator degrees of freedom and correcting for bias in the estimated variance-covariance of the fixed effects will be used. An unstructured covariance structure for the R matrix will be used by specifying 'type=UN' on the REPEATED line. 
 In the event that this model fails to converge, alternative correlation structures may be considered such as Compound Symmetry Heterogeneous (CSH) or Compound Symmetry (CS). Akaike's Information Criteria (AIC) will be used to assist with the selection of covariance structure. Distributional assumptions underlying the model used for analysis will be examined by obtaining a normal probability plot of the residuals and a plot of the residuals versus the fitted values (i.e. checking the normality assumption and constant variance assumption of the model respectively) to gain confidence that the model assumptions are reasonable. If there are any departures from the distributional assumptions, alternative models will be explored using appropriate transformed data or appropriate non-parametric methods may be explored.

[figure not shown]

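### A mixed meal test stopped at 15 or 30 minutes can enter the primary model as a 2-hour C-peptide mean; the effect on the result is probably small and the remedy is cheap

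*SAP*

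**What the plan says.** The primary endpoint is the change from baseline to Week 52 in stimulated C-peptide AUC over 0 to 120 minutes, divided by time so that it reads as a mean concentration (SAP 11.5.4). Samples are scheduled at -10, 0, 15, 30, 60, 90 and 120 minutes.

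- **Minimum for an AUC.** SAP 11.5.4: "there must be a minimum of one fasting data point (assessments scheduled for -10 minutes and Time 0), and one post-mixed meal data point". Protocol 8.3.5.9 has the same minimum and lists what counts after the meal: "one post-mixed meal data point (assessments scheduled for 15, 30, 60, 90, and 120 minutes". The two documents agree.
- **Divisor.** It is 120 minutes if the 120-minute result exists; "otherwise the time difference between first and last times with non-missing results is used" (SAP 11.5.4).
- **Exclusion.** For a test that meets the minimum, the only stated ground for dropping it is a finger-stick glucose outside the permitted range.
- **Historical control.** SAP 4 (DEFEND-1 Study) states that the DEFEND-1 AUC needed at least one sample before and at least two after the meal. Those data supply the prior: "The historical prior will be specified as Normal (-0.269, SE=0.043") (SAP 7.1.2).
- **Checks listed.** If much is missing, SAP 7.1.2 contrasts subjects without the value and subjects who have it: "the baseline characteristics of the subjects whose Week 52 mixed meal-stimulated C-peptide AUC is missing will be compared". SAP 11.4.3 has a general provision, applied where judged suitable, on this: "The impact of any major deviation from the planned assessment times and/or scheduled visit days on the analyses and interpretation of the results". SAP 11.9.1 lists residual plots for the MMRM. For the Bayesian primary model the stated check is: "Convergence of the Bayesian model will be assessed as described above".

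**The concern.** C-peptide rises over the two hours after the meal. The mean of the first 15 or 30 minutes is close to fasting and does not estimate the 2-hour stimulated mean. The minimum and the divisor together let such a value into the model under the 2-hour label.

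A truncated post-baseline test lowers that subject's change at that visit. A truncated baseline test raises the change at every visit. The runs with w=0 and w=1 and the non-Bayesian MMRM all use the same AUC, so none of them would show the problem. The missing-data comparison looks only at subjects whose AUC is missing, and here it is present.

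The trial is also looser on this point than its own historical control. Matching DEFEND-1 would not be enough, because samples at 0, 15 and 30 minutes would still pass.

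**Working it through.** **1. The plan's own figure.** Inputs from protocol 8.2.1: 45 and 15 evaluable subjects, SD 0.31, two-sided 0.05, difference 0.30, no historical data. SE = 0.31 × √(1/45 + 1/15) = 0.0924. Power = Φ(0.30/0.0924 − 1.96) = Φ(1.286) = 90.1%. Minimal detectable difference = 1.96 × 0.0924 = 0.181. Both match the stated 90% and 0.18.

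**2. Weight on the fasting value.** In the trapezoidal mean, Time 0 has half the first interval divided by the total interval. Full test: 7.5/120 = 6.25%. Samples at 0 and 15 only: 7.5/15 = 50%. Samples at 0, 15 and 30: 7.5/30 = 25%. This step uses only the SAP formula.

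**3. Error for one subject.** The documents give no C-peptide time course, so every profile below is an assumption.

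*Varying the size of the rise* (fasting 0.30, peak 1.5, 2.3 or 3.2 times fasting near 90 minutes): the full means are 0.409, 0.574 and 0.746. With 15-minute values of 0.34, 0.38 and 0.42, a 0/15 test gives (0.30 + 0.34)/2 = 0.32, 0.34 and 0.36. The errors are −0.09, −0.23 and −0.39 nmol/L, or 0.3 to 1.25 SD.

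*Varying the timing* (nmol/L at 0, 15, 30, 60, 90, 120 minutes):
- A: 0.30, 0.40, 0.55, 0.80, 0.90, 0.85
- B: 0.30, 0.50, 0.75, 0.90, 0.75, 0.60
- C: 0.30, 0.60, 0.85, 0.80, 0.60, 0.45

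| Samples available | A | B | C |
|---|---|---|---|
| All | 0.703 | 0.709 | 0.659 |
| 0, 15 | 0.350 (−50%) | 0.400 (−44%) | 0.450 (−32%) |
| 0, 15, 30 | 0.412 (−41%) | 0.512 (−28%) | 0.588 (−11%) |
| 0, 120 | 0.575 (−18%) | 0.450 (−37%) | 0.375 (−43%) |

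The last row shows that a late sample alone is no safeguard: it draws a straight line under the peak. The 0/15/30 row shows that two post-meal samples alone are not enough.

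**4. Effect on the estimates of one Week 52 test**, using the error of 0.353 from profile A:
- Placebo mean without historical data: 0.353/15 = 0.024.
- Albiglutide mean: 0.353/45 = 0.008.
- Placebo estimate when the historical component dominates, no covariates: prior precision 1/0.043² = 540.8; data precision 15/0.31² = 156.1; prior share 540.8/696.9 = 0.776; shift 0.0235 × 0.224 = 0.005.

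The third figure is the relevant one for placebo in the primary analysis. With w = 0.5 and a weakly informative component of SE 1000, the historical component keeps over 99% of the posterior weight until the placebo mean lies about 0.27 nmol/L from DEFEND-1.

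For several tests without historical data, the steepest profile gives 2 × 0.386/15 = 0.05 for two placebo tests and 3 × 0.386/45 = 0.026 for three albiglutide tests. SAP 7.1.1.1 sets thresholds at 0.1 and 0.2.

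**5. The proposed minimum** (fasting; 30 or 60; 90 or 120). Of the 31 possible post-meal sample patterns, the current minimum accepts all 31 and the proposed one accepts 18. Under A to C the error range narrows from −50% to +7% to −12% to +7%. With a sharp 60-minute peak (0.30, 0.35, 0.50, 1.20, 0.80, 0.50), samples at 0, 15, 30 and 120 still pass and give 0.469 against 0.719, or −35%.

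**6. Cost in power.** Losing one placebo Week 52 value (45 against 14): SE = 0.0949, power at 0.30 without historical data 88.5%.

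**The case against.** The case against acting is substantial. The protocol and SAP agree, so there is no contradiction, and where to set a minimum is a judgement. Nothing shows that a truncated test exists. The SAP reports other problems found on data review, such as the changed glucagon quantification limit, and none about test completeness. All error sizes rest on assumed profiles. The primary estimate moves by only 0.005 to 0.008 per test. The deviation review before unblinding (SAP 4.1) could pick up an aborted test. The proposed rule would make post-baseline AUCs stricter than those in DEFEND-1 and would leave truncated baselines in place. SAP 2.1 also wants analyses kept to a minimum.

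Most of this stands as to size, and the fix below is trimmed accordingly. It does not remove the defect. The current minimum is a stated rule that yields a wrong value, and the deviation review may list such a test but does not take its AUC out of the model. The general check in SAP 11.4.3 has no specified action, and the checks that involve "obtaining a normal probability plot of the residuals and a plot of the residuals versus the fitted values" are listed for the MMRM and not for the Bayesian model.

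A reader might infer that the primary result is materially biased, or biased in a known direction. The documents do not support that: the number of incomplete tests, their split by arm and whether they fall at baseline or follow-up are all unknown. A reader might also take 12% as the most that can go wrong under the new minimum. That holds only for profiles A to C.

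**Conclusion.** The point holds as a low-cost improvement to the derivation of the primary endpoint. That a test stopped at 15 or 30 minutes is accepted and labelled as a 2-hour mean follows directly from the SAP formula, with no assumption. For one subject the error can be about the size of the planning SD. The range of −0.09 to −0.39 nmol/L depends on the assumed profiles and is not a limit.

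The effect on the primary result is probably small if only a few tests are affected: about 0.005 or 0.008 nmol/L per Week 52 test, and about 0.024 for a placebo test in the analyses without historical data. These figures assume an error of 0.353, no covariate adjustment and, for the first, a dominant historical component. If no test was truncated, the amendment changes no result.

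**What to change.** Before unblinding, amend SAP 11.5.4 and record the change in SAP Table 1:

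- Calculate a post-baseline C-peptide AUC only with a fasting value, at least one value at 30 or 60 minutes and at least one at 90 or 120 minutes. Otherwise set it to missing under the missing-at-random model already specified in SAP 7.1.1.1.
- Keep incomplete baseline AUCs as now derived. Under SAP 11.4.2.2 a missing baseline leaves no change score, so the subject would be lost.
- Keep ITT membership on the current minimum and leave the DEFEND-1 prior as specified.
- State openly that baseline and DEFEND-1 AUCs then follow looser rules than post-baseline ones.
- State whether the rule also covers the glucagon AUC, which is derived in the same way, and flag maximum C-peptide taken from incomplete tests.
- Report incomplete tests by arm and visit. Only if any exist, repeat the primary Bayesian analysis once on the current minimum throughout and once without subjects whose baseline test fails the new one.

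The cost is one rule, one flag, one count table, one Table 1 entry and at most two further runs of the Bayesian model. The downside is that a few partial tests become missing. Missing at random may not hold if a test stopped because of intolerance; the run on the current minimum shows how much that matters. Losing one placebo value lowers power at 0.30 without historical data from about 90% to 88.5%, before any information recovered from the other visits.
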